#### 3.2 Rationale for Study Design

A randomized, double-blind study in healthy subjects is considered appropriate to evaluate the safety, tolerability, and PK of ISLA101. Single ascending doses of ISLA or placebo will be administered under fasting conditions, and safety and tolerability data will be evaluated in each cohort to guide doses administered to future cohorts. The highest tolerated dose will also be administered under fed conditions to assess any potential food effect (in a crossover manner). A rationale for dose selection is provided in Section 3.2.1.

#### 3.2.1 Dose Rationale for SAD

The starting dose of 300 mg/m^2 was selected based on the safety profile of fenretinide, which was extensively studied in multiple animal species in IND 38892:

# • Single-dose oral toxicity studies (Good Laboratory Practice [GLP]):

- Obes: doses up to 3000 mg/kg (human equivalent dose [HED] = 61666.7 mg/m^2); the maximum determinable non-lethal dosage was > 1350 mg/kg (HED = 27750 mg/m^2); observed clinical signs included emesis (> 2000 mg/kg), black tarry stool (2000 mg/kg), and loose stool (1350 mg/kg).
- Rats: dose of 5000 mg/kg (HED = 29838.7 mg/m^2); the median lethal dose was > 5000 mg/kg; clinical signs included diarrhea, unkempt appearance, yellow stool, hunched posture; no mortality was observed.
- Mice: dose of 7000 mg/kg (HED = 21056.9 mg/m^2); no clinical signs or mortality were observed.

These studies provided safety margins for the 300 mg/m^2 ISLA101 starting dose ranging from 70.2- to 99.5-fold.

# • Repeat-dose oral toxicity studies (GLP):

- Dogs: doses up to 800 mg/kg/day (HED = 16444.4 mg/m²). The no-observed-adverse-effect levels (NOAEL) from these studies were 90 mg/kg (HED = 1850 mg/m²) for a 12-month study, 600 mg/kg (HED = 12333.3 mg/m²) for a 20-day study, and 800 mg/kg (HED = 16444.4 mg/m²) for a 3-month study.
- ° Rats: doses up to 800 mg/kg/day (HED =  $4774.2 \text{ mg/m}^2$ ). The NOAEL from these studies was 800 mg/kg (HED =  $4774.2 \text{ mg/m}^2$ ) for a 3-month study and 70 mg/kg (HED =  $417 \text{ mg/m}^2$ ) for a 12-month study.

Although ISLA101 is not intended for chronic use, studies for up to 3 months in IND 38892 provide safety margins for a ISLA101 starting dose of 300 mg/m^2 ranging from 15.9- to 54.8-fold.

Therefore, in this study, a starting dose of 300 mg/m^2 is believed to be safe for administration to healthy subjects.

The starting dose and systemic safety of ISLA101 for the SAD study will be based on the rationale that the highest exposure in humans in the SAD study will not exceed the exposure levels derived in the nonclinical studies. Human equivalent doses of the NOAEL of selected studies with related exposure caps are shown in Table 3.

Table 3 Summary of Fenretinide NOAEL Data and PK Exposures to be Used to Determine Starting Dose and Exposure Caps in the ISLA101 Study

Species	Duration (weeks)	NOAEL (mg/kg/day)	Through Concentrations (ng/mL; mean ± SD)	C max (ng/mL; mean ± SD)	Human Equivalent Dose* (mg/m²)
Dogs (Study 1084)	12	800	1383 ± 908 (male); 819 ± 294 (female)	$2299 \pm 1456$	16444.4
Rats (Study 1077)	12	800	$183 \pm 83 \text{ (male)};$ $186 \pm 82 \text{ (female)}$	NA	4774.2

\* Assumes a 60 kg human.

NA = not available; NOAEL = no-observed-adverse-effect level; SD = standard deviation

The doses in this study were chosen based on the dose-response relationships described in nonclinical mouse models of dengue fever, and on the correlation between nonclinical and clinical exposures to fenretinide. In vivo, an oral fenretinide at 20 mg/kg (HED =  $60.2 \text{ mg/m}^2$ ) given at the time of infection and BID for 5 days protected 70% of mice from death (Fraser et al., 2014). At 180 mg/kg (HED =  $541.5 \text{ mg/m}^2$ ), given 24 hours prior to 10 days post-infection, there was a significant reduction in mice peak viremia (Carocci et al., 2015). In vitro and ex vivo, concentrations from 5 to 10  $\mu$ M exhibited highly specific and potent anti-dengue virus activity, with an average EC50 of 1.6  $\mu$ M and EC90 of 2  $\mu$ M (Fraser et al., 2014; Carocci et al., 2015). In humans, plasma concentrations produced by doses near 300 mg/m² ranged from 0.87 to 2.8  $\mu$ M, and by doses near 600 mg/m², from 2.1 to 5.2  $\mu$ M. The doses selected for inclusion in this study are therefore expected to be therapeutically relevant for the treatment of dengue fever.

#### 3.3 Dose and Dosing Regimen

The starting dose for the SAD study is 300 mg/m². The proposed dose escalation paradigm for SAD is shown in Table 4. Briefly, the doses to be tested are 300 mg/m² (fasted), 600 mg/m² (fasted), and 900 mg/m² (fasted). The highest tolerated dose level cohort will then be evaluated in a fed condition. Subjects will initially receive a dose of 300 mg/m², and the decision to advance to the next cohort will be based on safety and tolerability data.

Table 4 Proposed Single Ascending Dose Escalation

Cohort 1	Cohort 2	Cohort 3
$300 \text{ mg/m}^2$	$600 \text{ mg/m}^2$	$900 \text{ mg/m}^2$

Actual doses may be decreased from the planned doses based on emerging safety and tolerability data, as recommended by the independent SRC and agreed by the Investigator

and Sponsor. The initiation of the next cohort with a higher dose level will be decided during the interim safety review by the SRC. The recommendation of the SRC will be documented in a memo that will be filed in the Trial Master File (TMF). The SRC memo will serve as a source document for the clinical study report (CSR) and all supporting information can be presented to the human research ethics committee (HREC) if required. A description of the SRC is provided in Section 3.6.1.

If an acceptable safety profile is demonstrated in the previous cohort, enrollment of the next higher dose cohort may begin. For dose progression to occur, a minimum number of 7 subjects per cohort must have data from at least 96 hours after dosing, to ensure availability of placebo data.

Additional cohorts may be added as needed to test lower or repeat doses. Any changes to the dosing will made following discussions between the Sponsor and Investigator. The number of added cohorts will not exceed four. If the decision to enroll additional cohorts is made, an amendment will be submitted describing the safety and PK data from the portion of the study conducted to date. Enrollment of any additional cohorts will be initiated following HREC review and approval. The timing of vital sign assessment and PK sampling may be modified by SRC based on the emerging data after SAD dosing.

The incidence and nature of any AEs, dose-limiting AEs, SAEs, vital sign changes, and laboratory abnormalities will be assessed on an ongoing basis by SRC. Depending on the severity of these and/or other AEs or the occurrence of more than 1 AE in the same subject, the subject(s) may be unblinded if it is deemed necessary for the treatment of AEs.

# 3.4 Study Duration and Dates

The study will involve participation for a total of approximately 6 weeks. This includes up to 28 days for screening and approximately 5 days of confinement, and up to 3 days of follow-up after discharge from the clinic. For subjects in Cohort 4 (the food effect cohort), there will be an additional up to 5 days of confinement, and up to 3 days of follow-up.

#### 3.5 End of Study

The clinical study is considered completed when the last subject's final study visit has been completed.

#### 3.6 Study Oversight

The study will be overseen by the Sponsor or an appropriate designee.

#### 3.6.1 Safety Review Committee

An SRC will be comprised of, but not limited to, the Investigator, Medical Monitor, and an independent clinical representative. Other members of the SRC will be added on an as need basis, such as a PK scientist. The SRC will be responsible for reviewing data and deciding on:

• The continued safety of the study subjects.

- The continued validity of the trial.
- The continued scientific merit of the trial.
- Recommended dose for next cohort, as applicable.

The SRC will facilitate management and identification of potential safety concerns, will review safety data, and will determine if dosing of each cohort should continue, if dose escalation should continue following completion of each cohort, or if dose de-escalation or repeating a dose level should be performed.

#### 4 STUDY POPULATION SELECTION AND WITHDRAWAL

#### 4.1 Study Population

This study will enroll up to 24 healthy, male and female subjects who are 18 to 65 years old at the time of consent. Subjects who withdraw or are removed from the study, except for safety reasons, may be replaced at the discretion of the Sponsor.

#### 4.2 Inclusion Criteria

Subjects must meet the following criteria to be enrolled in the study:

- 1. Healthy male and female volunteers not of childbearing potential who are 18 years to 65 years of age (inclusive) at the time of signing the informed consent form (ICF).
- 2. Females not of childbearing potential as defined in the following criteria:
  - a. History of hysterectomy.
  - b. Post-menopausal:
    - i. Natural post-menopausal females with at least 12 months from natural spontaneous amenorrhea and a serum follicle-stimulating hormone (FSH) concentration ≥ 40 IU/L.
    - ii. Post-surgical females must have undergone bilateral oophorectomy at least 6 weeks prior to study.
- 3. Male subjects with female partners of childbearing potential must agree to practice abstinence or use a combination of 2 of the following acceptable birth control methods during the study and for at least 90 days after dosing:
  - a. Partners with an intrauterine device (IUD) without hormones in place for at least 3 months.
  - b. Barrier method (condom or diaphragm) for at least 14 days prior to screening and for 90 days after dosing with study drug.
  - c. Partners using stable hormonal contraceptive for at least 3 months prior to the study and for 90 days after dosing with study drug.
  - d. History of vasectomy at least 3 months prior to signing the ICF.
- 4. Must be able to understand and provide signed informed consent for study participation.
- 5. Willing and able to comply with all scheduled visits, treatment plan, laboratory tests, and other study procedures.
- 6. Females must have a negative serum hCG pregnancy test at screening.
- 7. Body mass index (BMI)  $\geq$  18.0 to 32.0 kg/m^2 (inclusive) and a body weight  $\geq$  50 kg.
- 8. Normal renal function, defined as estimated glomerular filtration rate (eGFR)  $\geq$  70 mL/min/1.73 m^2 at screening and Day -1.

- 9. Clinical laboratory values should be within the laboratory's stated normal range. If not within this range, they must be without clinical significance, as determined by the Investigator.
- 10. No history of clinically relevant medical disorders.

#### 4.3 Exclusion Criteria

A subject will be excluded from the study if he or she meets any of the following criteria:

- 1. Known or suspected pregnancy (confirmed via a positive serum hCG pregnancy test at screening), planned pregnancy during the study period, nursing, or lactation.
- 2. Women of childbearing potential or men who intend to father a child or donate sperm during the study period, and for 3 months after dosage of study drug.
- 3. Known allergy to fenretinide or any of the components of ISLA101.
- 4. Evidence or history of clinically significant medical conditions, such as hematological, renal, endocrine (e.g., polycystic ovarian syndrome PCOS or other anovulatory states), immunologic, pulmonary, metabolic, gastrointestinal (e.g., Crohn's disease, acute or chronic pancreatitis, and others), and surgery (except for simple appendectomy or repair of a hernia), which all can influence the absorption of study drug; cardiovascular, hepatic, psychiatric, neurologic, or allergic disease (including drug allergies but excluding untreated, asymptomatic, seasonal allergies at the time of dosing), or any other illness that the Investigator considers exclusionary or that could interfere with the interpretation of the study results.
- 5. History of severe infectious disease or recurrent infections.
- 6. Aspartate transaminase (AST), alanine aminotransferase (ALT), or total bilirubin above the 1.5 x upper limit of normal (ULN) at screening and Day -1.
- 7. Clinically significant electrocardiogram (ECG) abnormalities or vital sign abnormalities at screening and Day -1, long QT syndrome, or a history of cardiac disease.
- 8. Abnormal diet that may affect absorption, distribution, metabolism, or excretion of drugs, for example, lacking standard nutrients (e.g., cleansing diet 2 weeks before or during the study).
- 9. Positive result for hepatitis B, hepatitis C, or human immunodeficiency virus (HIV) at screening.
- 10. History of positive tuberculosis (TB) test at screening.
- 11. Has donated 1 unit of blood of over 500 mL within 56 days prior to the study drug administration, or donated plasma within 14 days of study drug administration.
- 12. Use of antibiotics within 30 days prior to dosing.
- 13. Use of drugs that inhibit or induce CYP enzymes within 30 days prior to administration of study drug and for the duration of study participation.
- 14. Use of tobacco products, e-cigarettes, and/or nicotine replacement products in the 3 months before screening.

- 15. Any food allergy, intolerance, or restriction that, in the opinion of the Investigator, could contraindicate the subject's participation in this study.
- 16. Recent history of (within the past 12 months), or strong potential for, alcohol or substance abuse. Alcohol abuse will be defined as > 14 drinks per week (1 drink = 10g of ethanol).
- 17. History of drug or alcohol abuse within 5 years before screening or positive result of UDS (e.g., amphetamines, benzodiazepines, cannabinoids, cocaine, hallucinogens, opiates) at screening, or alcohol breath test at screening or Day -1.
- 18. Exposure to any investigational agent or used an invasive investigational medical device within 30 days or within a period less than 5 drug half-lives prior to study entry (whichever is longer).
- 19. Study site employees, Sponsor's employees, or immediate family members of a study site or Sponsor employee.
- 20. Previously enrolled in this study.
- 21. Vaccination within less than 14 days from screening or plans to get a vaccine within 30 days after dosing.
- 22. Have an acute infection (such as influenza) or relevant lesion at the time of screening or admission. Subjects can be rescreened once they have recovered.
- 23. Criteria at the discretion of the Investigator:
  - a. Chronic medical condition that impacts subject safety.
  - b. Clinically significant abnormal physical examination or vital signs at screening.
  - c. Condition believed by Investigator to interfere with the subject's ability to provide informed consent or comply with study instructions, or that might confound the interpretation of the study results or put the subject at undue risk.
  - d. History or evidence of a clinically significant disorder, condition, or disease that that is believed by Investigator to significantly impair pain perception (e.g., history of stroke, history of neuropathy), would pose a risk to subject safety or interfere with evaluation, procedures, or study completion.

#### 4.4 Discontinuation of Treatment and Withdrawal of Subjects

Subjects are free to withdraw from the study at any time for any reason. Subjects who withdraw from the study early will be asked to complete the Early Termination procedures, as described in Table 1.

In addition, subjects are required to be withdrawn from the study by the Principal Investigator or sub-Investigator for the following reasons:

- Any unacceptable or intolerable AEs
- Difficulties in blood collection
- Non-compliance with study restrictions

- Study terminated by Sponsor
- Personal decision by the subject
- A subject who vomits immediately after study drug administration or up through 6 hours after administration or within  $2 \times T_{max}$  (once the  $T_{max}$  is known) after dosing.

The CSR will include reasons for subject withdrawals as well as additional details relevant to the subject withdrawal. Withdrawn subjects can be replaced if timing permits unless the withdrawal happened due to safety reasons related to the drug.

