Subjects will be discharged from the clinic on Day 5. At the discretion of the Investigator or designee, the confinement time can be extended to ensure the safety of each subject. Subjects will have up to 3 days of follow up. For Cohort 4 (the food effect cohort), the confinement and follow-up visit will be repeated. Subjects who are dosed but withdrawn prior to study completion will participate in an Early Termination visit and may be replaced if needed to obtain sufficient information as possible based on the timing.

In all cohorts, safety will be assessed via vital signs, clinical laboratory tests, physical examinations, AEs, and TEAEs. Pharmacokinetic data will be collected and analyzed at the end of the study but will not be used for dose escalation decisions. A description of study assessments is provided in Table 1.

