#### 4.4.1 Documenting Subject Withdrawal

If a subject prematurely withdraws from the study, either at her/his request or at the Investigator's discretion, the Investigator will record the reason for withdrawal on the relevant case report form (CRF) page. Subjects prematurely discontinuing the study, regardless of cause, should have all Early Termination study assessments performed.

It is important to obtain follow-up data for any subject withdrawn because of an AE, or abnormal laboratory test, vital sign measurement, or physical examination. In any case, every effort must be made to undertake safety follow-up procedures.

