## 8.1.4 Early Termination/Safety Follow-up Visit

At follow up or at early withdrawal from any cohort, subjects will complete the Follow-up/ET visit. Vital signs and temperature will be measured, and clinical laboratory tests will be performed. A physical exam will be performed, and clinically significant abnormalities will be reviewed by the Investigator. For females, urine pregnancy test will be performed. A review of AEs and concomitant medications will be performed.

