#### 8.1.5 Unscheduled Assessments

If a subject reports any AE(s) that present cause for concern during the study, they may be asked to complete further assessments. Any other procedures necessary to monitor the AE may be performed at the Investigator's discretion.

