## 8.2 Safety Assessments

This study is designed to assess the safety of ISLA101. Safety will be determined by evaluating physical examination findings, vital signs, clinical laboratory parameters, AEs, and TEAEs. Scheduled safety assessments will be performed at the time points shown in Table 1. If deemed necessary, additional safety measurements will be performed at the discretion of the Investigator, or Sponsor representative.

Adverse events will be assessed as described in Section 9.

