# 9.1.1.1 Reporting Adverse Events

All AEs, whether or not they are considered by the Investigator to be related to the study drug, must be recorded in the subject's source documents and in the electronic CRF. For each AE, the reported term, onset and end dates, severity, consequences on study drug intake (action taken), relationship to study drug, treatment provided, outcome, and information on seriousness of the event will be recorded.

The severity of the AE, relationship of the AE to study drug, and the outcome of the AE will be assessed by the Investigator.

Subjects will be monitored throughout the study for adverse reactions to the study drug and/or procedures. The subjects will be instructed to inform the study staff of any AEs that may occur at any time during the study. Observation of AEs extends from the time of ICF signing until the subject has left the study. Any AEs presenting within 30 days after the last scheduled visit will be followed up with a phone call or a visit until an outcome has been determined. After that time point, the need for additional follow-up of ongoing AEs or SAEs will be discussed between the Investigator and Sponsor.

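### Section 4.4 requires withdrawal from the study, not only from PK evaluation, for early vomiting or an intolerable AE, so the scheduled safety assessments after the single fasted dose are not assured in those subjects

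*Protocol*

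**What the plan says.** Protocol 4.4 states that "subjects are required to be withdrawn from the study by the Principal Investigator or sub-Investigator for the following reasons". The list includes unacceptable or intolerable AEs and "A subject who vomits immediately after study drug administration or up through 6 hours after administration", with an alternative limit of twice Tmax once Tmax is known. Withdrawal is from the study, and no lesser step such as leaving PK evaluation is offered.

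The protocol makes these provisions for a withdrawn subject:
- **Early Termination visit (8.1.4):** "At follow up or at early withdrawal from any cohort, subjects will complete the Follow-up/ET visit". It covers vital signs, laboratory tests, physical examination, a urine pregnancy test for females, AEs and concomitant medication. Neither 8.1.4 nor the Follow-up/ET column of Table 1 includes an ECG.
- **Safety follow-up (4.4.1):** follow-up data are called important after withdrawal for an AE or an abnormal finding, and "In any case, every effort must be made to undertake safety follow-up procedures".
- **AE follow-up (9.1.1.1, 9.1.8, 8.2.3):** "Any AEs presenting within 30 days after the last scheduled visit will be followed up with a phone call or a visit". AEs are followed until normal or acceptable, and verified clinically significant laboratory abnormalities until acceptable or explained.
- **Discretionary measures:** "At the discretion of the Investigator or designee, the confinement time can be extended to ensure the safety of each subject" (3.1); "Any other procedures necessary to monitor the AE may be performed" (8.1.5); "If deemed necessary, additional safety measurements will be performed at the discretion of the Investigator" (8.2).
- **Confinement (8.1.2):** all subjects stay in the unit up to Day 5. The section does not say whether this includes withdrawn subjects, or whether their scheduled assessments continue.

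SAP 3.2 treats vomiting as a possible PK problem to be assessed subject by subject, with vomiting within 2 hours of the dose as its example.

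**The concern.** Each cohort receives one dose (5.1.2), so withdrawal after that dose spares the subject no further fasted exposure. Only the recalled cohort has a later, fed dose that withdrawal could prevent (3.1, 6.1). The primary objective is safety and tolerability under fasted conditions (2.1.1), and protracted nausea and vomiting is itself an AE of special interest (9.1.5). The rule therefore takes off the planned schedule the subjects who say most about tolerability.

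Neither reason for withdrawal requires this. A PK profile impaired by vomiting is a reason to leave the PK analysis. An intolerable AE is a reason for more observation. What is at stake is completeness of the planned vital signs, laboratory tests and ECG in a few subjects in cohorts of 8 (6 active, 2 placebo).

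**Working it through.** The plan gives no figure to reproduce: there is no sample-size calculation (10.2) and no assumed vomiting or withdrawal rate. The check compares what Table 1 schedules after dosing in Cohorts 1 to 3 with what remains assured after withdrawal.

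**Inputs**
- Withdrawal window for vomiting: to 6 hours, or twice Tmax once known (4.4). The 6-hour limit is used here.
- Scheduled observation reviewed for escalation: to 96 hours (3.3, 5.2).
- Vital-sign visits after Day 1: Days 2, 3, 4, 5 and 8, which is 5 (Table 1).
- Laboratory visits after Day 1: the same 5 days in Table 1, with 8.1.3.1 also covering Days 1 to 5. The blood-volume text in 8.3 lists only Days 2, 3 and 8 after Day 1, which is 3.
- Post-dose ECG: one time point, 5 hours on Day 1 (Table 1, note 2). The SAP shell for Table 14.3.6.1.1 has no other post-dose row.
- Assured after withdrawal: one Early Termination set, without ECG (8.1.4, Table 1).

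**Upper-bound counts, assuming the subject leaves at withdrawal**
- Observation time, withdrawal at 6 hours: 96 − 6 = 90 hours not assured. With earlier withdrawal the figure is larger.
- Vital signs, counting the Early Termination set as one of the five: 5 − 1 = 4 of 5 not assured.
- Laboratory tests: 5 − 1 = 4 of 5 on the Table 1 schedule, or 3 − 1 = 2 of 3 on the draw days in 8.3.
- ECG, withdrawal before 5 hours: 0 of 1 post-dose time points assured. The 5-hour reading falls inside the 6-hour window.

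**Whether the other provisions restore the schedule**
- 8.1.4 places the Early Termination visit at withdrawal, so it can fall on Day 1.
- 9.1.8 follows the event until it is normal or acceptable. A short vomiting episode can meet that within hours, after which 9.1.8 requires no further scheduled visits.
- 4.4.1 does not say which procedures are meant or how often.
- 3.1, 8.1.5 and 8.2 allow more observation but do not require it.
- 8.1.2 may keep the subject in the unit, but does not say that a withdrawn subject continues the timetable.

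Together these make continued observation likely. None of them assures the Day 2 to 5 and Day 8 assessments or the 5-hour ECG.

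**The case against.** The strongest reply is that both triggers are AEs, so follow-up is directed at exactly these subjects. Sections 4.4.1, 8.2.3 and 9.1.8 call for it, and 8.1.2 confines all subjects to Day 5. The event is recorded, the subject stays in the Safety Population (10.3; SAP 3.1), and the Early Termination visit covers the kinds of data named as primary endpoints. ECG is not among those endpoints (2.1.2). All of this stands. A reader might infer that safety observation ends at withdrawal, and the documents do not support that. What is unprotected is the fixed timetable.

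Two other stronger readings also fail:
- **That the 6-hour limit is the only one that can operate, because PK is analysed at the end of the study.** Section 4.4 does not confine Tmax to this study, 1.2.1 refers to five earlier clinical pharmacology studies, and 3.3 foresees an amendment describing PK data to date if cohorts are added.
- **That two such withdrawals would block escalation under the 7-subject rule in 3.3.** Withdrawn subjects may be replaced (3.1, 4.4, 4.5) unless the reason is safety.

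It can also be said that withdrawal already keeps these subjects out of the fed period. That is true, and it is why the Cohort 4 sentence is needed once the withdrawal rule is relaxed.

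**Conclusion.** The point holds as a low-cost improvement, one to consider; it does not demonstrate a hazard. Following 4.4 as written can cut short planned safety data in the subjects most informative about tolerability, and no other section guarantees that the schedule continues. Confidence in the reading of 4.4 is high.

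The size is bounded only from above: 90 of 96 hours for withdrawal at 6 hours, 4 of 5 later vital-sign visits, 4 of 5 (or 2 of 3) later laboratory visits, and the single post-dose ECG if withdrawal comes before 5 hours. All of these assume that the subject leaves at withdrawal. Continued confinement or discretionary assessments would reduce them, possibly to nothing. No expected number of affected subjects can be given.

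**What to change.** - **4.4, vomiting:** make vomiting within the window a reason for exclusion from PK evaluation, consistent with the case-by-case assessment in SAP 3.2, and not a reason for withdrawal from the study.
- **4.4, safety schedule:** keep every consenting dosed subject, including those with intolerable AEs, on the safety assessments already scheduled, including the 5-hour ECG, through 96 hours and Day 8.
- **4.4 and the Cohort 4 recall text:** state that subjects with an intolerable AE, or without a usable fasted PK profile, are not re-dosed in Cohort 4. Judge usability without unblinding, from the vomiting window and missed samples, since PK analysis is planned for the end of the study (3.1).
- **4.5:** allow replacement of PK-non-evaluable subjects for PK purposes at the sponsor's discretion.

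The cost is protocol wording and a few subjects staying for assessments already planned for them. No new procedure is added, and subjects remain free to withdraw.
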